2. SYNOPSIS

Study Number and Title:

GBT021601-012: An Intrapatient Single Dose and Multiple Ascending Dose Study to Evaluate the Pharmacokinetics, Safety, Tolerability, and Pharmacodynamics of GBT021601, a Hemoglobin S Polymerization Inhibitor, in Participants with Sickle Cell Disease (SCD).

Study Short Title:

GBT021601-012 Single Dose and Multiple Ascending Dose in Participants with SCD.

Estimated Number of Study Centers and Countries or Regions:

Up to 3 sites in the United States of America.

Study Rationale:

This study will evaluate the pharmacokinetics (PK), safety, tolerability, and pharmacodynamics (PD) with a single dose followed by ascending, intrapatient doses of GBT021601, a hemoglobin S (HbS) polymerization inhibitor, in participants with SCD.

Objectives:**Primary**

- To evaluate the safety and tolerability of a single dose and multiple ascending doses of GBT021601 in participants with SCD.

Secondary

- To evaluate the PK of a single dose and multiple ascending doses of GBT021601 in participants with SCD.
- To evaluate the PD properties (effect on Hb oxygen equilibrium curves (OEC) as measured by % Hb modification and p50) of a single dose and multiple ascending doses of GBT021601 in participants with SCD.
- To confirm the relationship between time matched GBT021601 concentrations and the change from baseline or % change from baseline of clinical measures of anemia and hemolysis.

CCI

**Study Design:**

This is an open-label, intrapatient, single dose followed by a multiple dose escalation study in at least six (6) participants with SCD.

Single-dose Period (Part A)

After eligibility has been confirmed and the informed consent form signed, participants will be admitted into the clinical research unit (CRU) on the day prior to study drug administration (Day -1). On Day 1 a single oral dose of GBT021601 will be administered following an overnight fast of at least 10 hours and no food will be allowed for at least 4 hours postdose. A dose of 100 mg is planned but the decision regarding the actual study dose will depend on the findings in the single ascending dose

portion of the “first-in-human” (FIH) Study GBT021601-011. The dose will be no higher than a dose that has been well tolerated by the healthy participants in the FIH study. Participants will remain confined to the CRU until 72 hours after dosing (Day 4) and return for brief visits on Days 7, 14, 21, 28, and 42 (as outlined in the Schedule of Assessments).

Safety, tolerability, and PK data collected from Day 1 through Day 42 from a minimum of 4 participants will be required for the Safety Monitoring Committee (SMC) to make the decision to proceed to multiple ascending doses (Part B).

Multiple Ascending-dose Period (Part B)

Following a minimum of a 56-day washout from the single dose in Part A, participants will start the multiple ascending dosing (Part B). Depending on the observed half-life of GBT021601 in the FIH study, participants will receive a maintenance dose regimen which may or may not be preceded by a loading dose. The % Hb occupancy by GBT021601 will be calculated from the PK as the ratio of GBT021601 concentration to the Hb (estimated at 5mM) in RBCs. The Hb% modification will be based on hemoximetry data. The mg dose and dosing frequency will be determined by the PK results of GBT021601-011 and PK and hemoximetry results (occupancy/modification) from Part A. The predicted target for the first multiple dose regimen is ~20% to 30% hemoglobin (Hb) occupancy/modification. Participants will receive a maintenance dose through Week 10.

After the first multiple dose period, if the % Hb occupancy/modification is higher than 30 percent, the participant will remain on the same maintenance dose or have a dose increase that maintains the % Hb occupancy/modification at > 30%. If the % Hb occupancy is less than 30%, the participant will dose escalate at Week 13.

At the Week 13 Visit, eligible participants may be dose escalated to receive a loading dose and subsequent maintenance dose based on a predicted target of > 30% occupancy/modification. The mg dose and frequency will be determined by the PK results of GBT021601-011 and PK and hemoximetry results from Part A and Part B. Participants will receive maintenance doses through Week 16. Week 16 will be the end of treatment (EOT) Visit and participants will return to the clinical site for the end of Part B Safety Follow-up Visit approximately 5 half-lives (maximum of 120 days) after the final dose at the Week 16 Visit. The half-life will be determined from the PK results from the GBT021601-011 study and the PK results from Day 42 following the single dose (Part A) in this study. Participants will not be confined in the CRU during the Multiple Ascending-dose Period.

Extended Treatment Period (Part C)

As of Protocol Amendment 5, eligible participants may proceed with an Extended Treatment Period of at least 6 weeks, with a 300 mg loading dose twice daily over 4 days and subsequent maintenance dose of 150 mg once daily starting from Part C Day 1 and continuing through Part C Week 6. **CCI** [REDACTED]

Duration of Study Participation:

The maximum duration of the study is dependent on the half-life of GBT021601. At a minimum, the study duration will include a 28-day Screening period, an 8-week Single-dose Period, and a 6-week Multiple Ascending-dose Period for a total of 18 weeks. This will be followed by an EOB Visit 5 half-lives after the final dose of GBT021601. It is anticipated that 5 half-lives will not exceed 120 days after the final dose. Therefore, the maximum duration for a participant will be approximately 218 days or approximately 31 weeks.

As of Protocol Amendment 5, the maximum duration of the study will be approximately 53 Weeks, which includes the approximately 6-week Extended Treatment Period, and a 4- and 8-week follow up.

Number of Participants:

At least six (6) participants with SCD. Participants in Part A (single dose) will continue to Part B (multiple ascending-dose). As of Protocol Amendment 5, all eligible participants will proceed with the extended treatment period (Part C).

Participant Selection Criteria:

Participants with SCD ages 18 to 60 years, inclusive.

Test Product, Dose, Route of Administration, and Duration of Treatment:

Single-dose Period (Part A)

- GBT021601 will be provided as a single dose, orally administered, 100 mg tablet.

Multiple Ascending-dose Period (Part B) and Extended Treatment Period (Part C)

- GBT021601 will be provided as orally administered multiple dose tablets and/or capsules for approximately 6 to 8 weeks (Part B) and for the approximately 6-week Extended Treatment Period (Part C).
- Loading and maintenance doses and frequency will be determined based on PK results from GBT021601-011 and on PK and /or hemoximetry results from Part A. Dose escalations will not exceed 2-fold the previous dose. For the Extended Treatment Period, the loading dose will be 300 mg, twice daily, for 4 days followed by a once daily maintenance dose of 150 mg.

Criteria for Evaluation:

Safety:

Participant safety and tolerability will be monitored during the study using standard measures, including physical examination, vital signs, 12-lead electrocardiogram, safety laboratory assessments (hematology measurements, chemistry measurements [including measures of hemolysis]), urinalysis, concomitant medication usage and adverse event monitoring.

Pharmacokinetics:

Plasma and whole blood concentrations of GBT021601 will be determined using validated assay methods. Red blood cell (RBC) concentrations will be calculated. The following whole blood, plasma, and RBC PK parameters of GBT021601 will be calculated, if appropriate. See below for PK parameters to be collected during each phase.

Single-dose Period (Part A): Maximum plasma/whole blood concentration (C_{max}), time of maximum serum concentration (t_{max}), area under the concentration vs time curve from time zero to 24 hours (AUC_{0-24}), area under the concentration vs time curve from zero to last quantifiable concentration (AUC_{0-t}), area under the concentration vs time curve from time zero extrapolated to infinity ($AUC_{0-\infty}$), apparent clearance (CL/F), apparent volume of distribution during the terminal phase (Vz/F), half-life ($t_{1/2}$) and % Hb occupancy.

Multiple Dose (Part B and Part C): Plasma/whole blood C_{max} , plasma/whole blood C_{min} , plasma/whole blood AUC at steady-state, half-life ($t_{1/2}$) and % Hb occupancy.

Pharmacodynamics (Parts A, B, and C):

Hemoximetry (the partial pressure of oxygen at which the hemoglobin protein is 20% and 50% saturated [p20 and p50, respectively]), RBC deformability, and serum erythropoietin will be measured. The relationship between time matched GBT021601 concentrations and the change from baseline or % change from baseline of clinical measures of anemia and hemolysis will be evaluated.

CCI

Planned Sample Size:

Due to the exploratory nature of this study, no formal power or sample size calculations were used to determine cohort size. A sample size of at least 6 participants with SCD are expected to provide adequate characterization of PK and safety for both the Single-dose Period and the Multiple Ascending-dose Period.

Statistical Analysis:

Adverse events will be coded to system-organ class and preferred term using the Medical Dictionary for Regulatory Activities (MedDRA) and summarized. Vital signs and laboratory safety assessments will be presented with identification of clinically significant values and those outside of normal range.

CC1 [REDACTED] Electrocardiogram data

will be presented with any clinically relevant abnormal findings or changes highlighted. The PK and PD parameters will be listed and summarized using appropriate descriptive statistics.

SCHEDULES OF ASSESSMENTS AND PROCEDURES

Table 1: Schedule of Assessments for Single-dose Period (Part A)

Study Day	Screen	Confinement					Outpatient				
	-30 to -2	-1	1	2	3	4	7	14	21	28	42
Informed consent	X										
Eligibility assessment	X	X									
Medical history ^a	X										
Physical examination ^b	X	X				X					
Height	X										
Weight	X	X				X	X	X	X	X	X
Vital signs ^c	X	X	X	X	X	X	X	X	X	X	X
12-lead ECG (triple tracing) ^d	X	X	X	X	X	X		X			X
Study drug administration			X								
Serology (hepatitis A, B, C) HIV, SARS-CoV-2	X										
Alcohol (breath or blood) and urine drugs of abuse screen	X	X									
Hematology, Serum chemistry, and Lipid Panel ^e	X	X		X		X		X		X	
aPTT, INR, PT	X										
Serum erythropoietin		X	X			X		X		X	
SCD documentation or Hemoglobin Electrophoresis	X										
eGFR ^f	X	X									
Urinalysis	X	X				X					
Pregnancy test (women only) ^g	X	X						X		X	
FSH (postmenopausal women only)	X										
Pharmacokinetic assessment (whole blood and plasma)			X	X	X	X	X	X	X	X	X
Hemoximetry			X	X		X	X		X		X
RBC deformability, dense cells ^h			X								

Study Day	Screen	Confinement					Outpatient				
		-30 to -2	-1	1	2	3	4	7	14	21	28
Concomitant medication	X	X	X	X	X	X	X	X	X	X	X
Adverse events	X	X	X	X	X	X	X	X	X	X	X

Abbreviations: aPTT, activated partial thromboplastin time; CoV, coronavirus; ECG, electrocardiogram; eGFR, estimated glomerular filtration rate; EOS, end of study; ET, early termination; FSH, follicle-stimulating hormone; HIV, human immunodeficiency virus; INR, International Normalized Ratio; PCR, polymerase chain reaction; PT, prothrombin time; RBC, red blood cell; SARs, severe acute respiratory syndrome; SCD, sickle cell disease.

^a History update, if any, will be obtained.

^b A full physical examination should be conducted at Screening. All subsequent physical examinations should be signs and symptoms driven.

^c Vital Signs include blood pressure, heart rate, respiration rate, body temperature while the participant is in a supine position. See [Table 2](#).

^d 12-Lead ECG on Day 1 should be performed within 30 minutes prior to dose, and 4 and 8 hours after dosing, then in the morning of each day of confinement and at any time at other clinic visits. See [Table 2](#).

^e The Lipid Panel is done at the Screening Visit only.

^f The eGFR will be calculated at Screening and confirmed on Day -1 using the Cockcroft-Gault formula.

^g A serum pregnancy test will be conducted at Screening and ET and urine pregnancy test at all other visits. A serum pregnancy test will also be conducted when a positive urinary pregnancy test occurs for confirmation.

^h RBC deformability and dense cells will be tested on Day 1 predose and 12 hours postdose.

Table 2: Schedule of Select Study Procedures (First 48 hours)

Procedure	Sampling Timepoint										
	Pre dose	Postdose (hours)									
		0.25 hr	0.5 hr	1 hr	2 hr	4 hr	6 hr	8 hr	12 hr	24 hr (Day 2)	36 hr
HR and BP ^{a, b}	X				X	X	X	X	X	X	X
RR and Body Temperature ^{a, b}	X									X	X
12-lead safety ECGs ^{b, c}	X			X		X		x		X	X
PK Sampling ^d	X	X	X	X	X	X	X	X	X	X	X

Abbreviations: BP, blood pressure; ECG, electrocardiogram; HR, heart rate; PK, pharmacokinetic; RR, respiratory rate; SAD, single ascending dose.

Note: For procedures scheduled to be performed at the same time, priority is to be given to collection of the PK samples at the designated time.

ECGs, followed by vital signs, are to be taken before PK sampling, unless PK samples will be late as a result. If times are delayed due to technical difficulties, this will be noted, but not considered a protocol deviation.

^a HR, BP, RR, and body temperature will be measured after a participant has rested for at least 5 minutes in the supine position.

^b Window for collection: up to 3 hours predose, \pm 15 minutes up to 12 hours post, \pm 30 minutes if \geq 24 hours postdose.

^c ECGs (12-lead) will be collected in triplicate within 5 minutes after a participant has rested at least 5 minutes in the supine position. Pre-dose ECGs and vital signs on Day 1 may be performed within 3 hours prior to dosing.

^d Predose blood PK sample to be collected within 60 minutes prior to dosing. Postdose collection windows are: 0.25, 0.5 and 1 hour \pm 2 mins, 2 to 24 hours \pm 5 mins, 36 and 48 hours \pm 10 mins.

Table 3: Schedule of Assessments for Multiple Ascending-dose Period (Part B)

Study Week	Week 8 (Day 56 + 4 weeks) ^a	Week 9 (Day 63 ± 3 days)	Week 10 (Day 70 ± 3 days)	Week 11 (Day 77 + 3 days)	Week 12 (Day 84 ± 3 days)	Week 13 (Day 91 ± 3 days)	Week 14 (Day 98) ± 3 days	Week 15 (Day 105) ± 3 days	Week 16 (Day 112) EOT	Every 4 weeks through EOB ± 7 days	Day 218 (EOB/ET)
Physical examination	X					X			X		X
Height											
Weight	X		X								
Vital signs ^c	X	X	X	X	X	X	X	X	X		X
12-lead ECG (triple tracing) ^d	X					X			X		X
Study drug administration	X ^e	X	X	X	X	X ^f	X	X	X		
Dispense patient diary ^g	X	X	X	X	X	X	X	X			
Collect patient diary ^g		X	X	X	X	X	X	X	X		
Hematology and serum chemistry	X		X		X	X		X	X	X	X
Blood smear ^h	X								X		X
Serum erythropoietin	X					X	X		X		
eGFR ⁱ	X					X					X
Urinalysis	X					X					X
Pregnancy test (women only) ^j	X					X					
Pharmacokinetic assessment (whole blood and plasma) ^k	X	X	X	X	X	X	X	X	X	X	X

Study Week	Week 8 (Day 56 + 4 weeks) ^a	Week 9 (Day 63 ± 3 days)	Week 10 (Day 70 ± 3 days)	Week 11 (Day 77 + 3 days)	Week 12 (Day 84 ± 3 days)	Week 13 (Day 91 ± 3 days)	Week 14 (Day 98) ± 3 days	Week 15 (Day 105) ± 3 days	Week 16 (Day 112) EOT	Every 4 weeks through EOB ± 7 days	Day 218 (EOB/ET)
Hemoximetry ^k	X	X	X			X		X	X		X
RBC deformability, dense cells (if feasible) ^k	X	X	X			X		X	X		X
Concomitant medications	X	X	X	X	X	X	X		X		X
Adverse events	X	X	X	X	X	X	X		X		X
Clinic visit	X	X	X	X	X	X	X		X		X

Abbreviations: ECG, electrocardiogram; eGFR, estimated glomerular filtration rate; EOB, end of Part B; ET, early termination; RBC, red blood cell.

Note: For procedures scheduled to be performed at the same time, priority is to be given to collection of the PK samples at the designated time.

ECGs, followed by vital signs, are to be taken before PK sampling unless PK samples will be late as a result

^a Week 8 (Day 56) is the first visit in the Multiple-Ascending-dose Period.

^b The Day 218 Visit will occur approximately 5 half-lives after the dose at Week 16.

^c HR, BP, RR, and body temperature will be measured after a participant has rested for at least 5 minutes in the supine position. Assessment of vital signs may be performed up to 3 hours predose.

^d 12-Lead ECG should be performed within 30 minutes prior to dose and will be collected in triplicate within 5 minutes after a participant has rested at least 5 minutes in the supine position.

^e Study drug will be administered as a loading dose of TBD mg and a maintenance dose of TBD mg every TBD (Dose 1) beginning at the Week 8 (Day 56) Visit. Participants will receive maintenance Dose 1 through Week 10. At the Week 8 Visit, the participant will remain in the clinic for 4 hours postdose for vitals, 12-lead ECG and AE assessment.

^f Study drug will be administered as a loading dose of TBD mg and a maintenance dose of TBD mg every TBD (Dose 2) beginning at the Week 13 (Day 91) Visit. Participants will receive maintenance Dose 2 through Week 16. At the Week 13 Visit, the participant will remain in the clinic for 4 hours postdose for vitals, 12-lead ECG and AE assessment

^g Site to dispense a new diary and collect the previous diary from the patient, when applicable. Diary to be collected only during the maintenance dosing when the participant is self-administering study drug at home. Participants should be instructed to complete the diary each week and return it at the next visit for site review.

^h A blood smear is to be performed before the Multiple Ascending Dosing Period Day 56 and Day 112 visits.

ⁱ The eGFR will be calculated using the Cockcroft-Gault formula.

^j A urine pregnancy test will be conducted. A serum pregnancy test will also be conducted when a positive urinary pregnancy test occurs for confirmation.

^k Samples for PK will be collected: predose, 0.25 to 1 hours postdose and 2 to 4 hours postdose. Sample collection times for hemoximetry and RBC deformability should be aligned with the predose PK sample and the 2 to 4 hour postdose PK sample. No 0.25 to 1 hour postdose sample shall be collected for hemoximetry or RBC deformability. The predose blood sample for PK and PD assessments should be collected within 30 minutes prior to dosing.

Table 4: Schedule of Assessments for Extended Treatment Period (Part C)

Study Day/Week	Part C Screening Visit (Day -28 to Day -1)	Part C Day 1	Part C Week 2 (Day 14 ± 3 days)	Part C Week 4 (Day 28 ± 3 days)	Part C Week 6 (Day 42) ± 3 days) EOET	Part C Week 10 (Day 70 ± 3 days)	Part C Week 14 (Day 98 ± 3 days)	Final Visit (EOS/CCI)
Informed Consent	X							
Eligibility confirmation ^a	X							
Physical examination	X				X		X	X
Weight	X	X			X		X	X
Vital signs ^b	X	X	X	X	X	X	X	X
12-lead ECG (triple tracing) ^c	X	X	X	X	X		X	X
Study drug administration ^d		X	X	X	X			
Dispense participant diary ^e		X	X	X				
Collect participant diary ^e			X	X	X			
CCI [REDACTED]	[REDACTED]	[REDACTED]	[REDACTED]	[REDACTED]	[REDACTED]	[REDACTED]		
[REDACTED]			[REDACTED]	[REDACTED]	[REDACTED]	[REDACTED]	[REDACTED]	[REDACTED]
Hematology and serum chemistry	X	X	X	X	X	X	X	X
Serum erythropoietin	X	X			X		X	X
eGFR ^f	X	X			X		X	X
Urinalysis	X	X			X		X	X
Pregnancy test (women only) ^g	X	X			X		X	X
Pharmacokinetic assessment (whole blood and plasma) ^h		X	X	X	X	X	X	X
Hemoximetry ^h		X		X	X		X	X

Study Day/Week	Part C Screening Visit (Day -28 to Day -1)	Part C Day 1	Part C Week 2 (Day 14 ± 3 days)	Part C Week 4 (Day 28 ± 3 days)	Part C Week 6 (Day 42) ± 3 days) EOET	Part C Week 10 (Day 70 ± 3 days)	Part C Week 14 (Day 98 ± 3 days)	Final Visit (EOS CCI)
RBC deformability, dense cells (if feasible) ^h		X		X	X		X	X
Blood smear		X			X		X	X
CCI		■			■			
Concomitant medications		X	X	X	X	X	X	X
Adverse events		X	X	X	X	X	X	X

Abbreviations: CCI ECG, electrocardiogram; eGFR, estimated glomerular filtration rate; EOET, End of Extended Treatment; EOS, end of study; ET, early termination; CCI RBC, red blood cell.

Note: For procedures scheduled to be performed at the same time, priority is to be given to collection of the PK samples at the designated time.

ECGs, followed by vital signs, are to be taken before PK sampling unless PK samples will be late as a result

^a For newly enrolled participants, the Screening Visit will be the same as that in Table 1.

^b HR, BP, RR, and body temperature will be measured after a participant has rested for at least 5 minutes in the supine position. Assessment of vital signs may be performed up to 3 hours predose.

^c 12-Lead ECG should be performed within 30 minutes prior to dose at Part C Day 1, Part C Week 2, and 4hrs post dose at Part C Weeks 4 and 6. All ECGs will be collected in triplicate within 5 minutes after a participant has rested at least 5 minutes in the supine position.

^d Study drug will be administered beginning at the Day 1 Visit as a loading dose of 300 mg twice daily for four days followed by a maintenance dose of 150 mg once daily through at least Part C Week 6 (if treatment will be extended beyond 6-weeks, additional study drug administration and Visits will be added). At the Part C Week 4 and Part C Week 6 Visits, the participant will remain in the clinic for 4 hours postdose for vitals, 12-lead ECG and AE assessment.

^e Site to dispense a new diary and collect the previous diary from the participant, per above. Diary to be completed throughout the study, except for the first loading dose and any maintenance doses administered in the clinic. The actual time of every dose administration should be recorded in the diary or at the clinic to enable PK calculations. CCI

^f The eGFR will be calculated using the Cockcroft-Gault formula.

^g A urine pregnancy test will be conducted. A serum pregnancy test will also be conducted when a positive urinary pregnancy test occurs for confirmation.

^h Samples for PK will be collected: prior to the first dose at Part C Day 1, Part C Week 2, Part C Week 4, Part C Week 6 as well as at 0.25 to 1 hours post-dose and 2 to 4 hours post dose on the Week 4 and Week 6 visits. Sample collection times for hemoximetry and RBC deformability should be aligned with the pre-dose PK sample and the 2 to 4-hour post-dose PK sample (for Week 4 and Week 6 visits). Refer to Table 12 for specifics. No 0.25 to 1 hour post-dose samples shall be collected for hemoximetry or RBC deformability. The predose blood sample for PK and PD assessments should be collected within 30 minutes prior to dosing.

LIST OF ABBREVIATIONS

The following abbreviations and specialist terms are used in this study protocol.

Abbreviation or Specialist Term	Explanation
ADLs	Activities of daily living
AE	Adverse event
ALT	Alanine aminotransferase
APTT	Activated partial thromboplastin time
AST	Aspartate aminotransferase
AUC ₀₋₂₄	Area under the concentration vs time curve from time zero to 24 hours
AUC _{0-t}	Area under the concentration vs time curve from zero to last quantifiable concentration
AUC _{0-∞}	Area under the concentration vs time curve from time zero extrapolated to infinity
BP	Blood pressure
BPM	Beats per minute
CCI	[REDACTED]
CL/F	Apparent clearance
C _{max}	Maximum plasma/whole blood concentration
C _{min}	Minimum plasma/whole blood concentration
CCI	[REDACTED]
CoV	Coronavirus
COVID-19	Coronavirus disease 2019
CRO	Contract research organization
CRU	Clinical research unit
CYP	Cytochrome P450
°C	Degrees Celsius
CCI	[REDACTED]
DILI	Drug-induced liver injury
ECG	Electrocardiogram
eCRF	Electronic case report form
eGFR	Estimated glomerular filtration rate
EOS	End of Study
EOT	End of Treatment
EPO	Erythropoietin
ET	Early Termination
FDA	(United States) Food and Drug Administration
CCI	[REDACTED]

Abbreviation or Specialist Term	Explanation
FIH	First-in-human
FSH	Follicle-stimulating hormone
GBT	Global Blood Therapeutics, Inc.
GCP	Good Clinical Practice
Hb	Hemoglobin
Hb-O ₂	Hemoglobin-oxygen
HbS	Sickle hemoglobin
HbSB	Double heterozygote for HbS and b-0 thalassemia
HbSS	Homozygous for sickle cell allele
HIV	Human immunodeficiency virus
HR	Heart rate
HU	Hydroxyurea
IgM	Immunoglobulin M
IB	Investigator's brochure
ICF	Informed consent form
ICH	International Conference on Harmonisation
INR	International Normalized Ratio
IRB	Institutional Review Board
MedDRA	Medical Dictionary for Regulatory Activities
NCI CTCAE	National Cancer Institute Common Terminology Criteria for Adverse Events
NOAEL	No-observed-adverse-effect level
CCI	[REDACTED]
CCI	[REDACTED]
OxyHb	Oxy-hemoglobin
PD	Pharmacodynamics
PK	Pharmacokinetics
PT	Prothrombin time
p20	Hemoglobin protein is 20% saturated
p50	Hemoglobin protein is 50% saturated
RBC	Red blood cell
RR	Respiratory rate
SAD	Single ascending dose
SAE	Serious adverse event
SARS	Severe acute respiratory syndrome
SCD	Sickle cell disease
SMC	Safety Monitoring Committee

Abbreviation or Specialist Term	Explanation
t_{max}	Time of maximum serum concentration
$t_{1/2}$	Half-life
ULN	Upper limit of normal
US	United States
Vz/F	Apparent volume of distribution during the terminal phase

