3.4.2.3. Rationale for Evaluation of Higher Dose of GBT021601

As of Protocol Amendment 5, after a total of 8 weeks of treatment, all participants in this study demonstrated improvements in hematologic parameters, including reticulocytes and absolute reticulocytes, lactate dehydrogenase, and indirect bilirubin (Brown, 2021). Preliminary findings indicate a dose-related mean increase from about 15% to 32% in Hb occupancy after dosing with 50 mg daily and 100 mg daily respectively. Preliminary clinical safety data show that GBT021601 has been well tolerated with no significant treatment-related safety findings reported. An extended treatment period evaluating a dose escalation to 150 mg once daily for at least 6 weeks preceded by a loading dose of 300 mg, given twice daily over 4 days (the loading dose is being administered twice daily to minimize the potential for any gastrointestinal effect

that could theoretically occur with a higher once daily loading dose) is targeted to increase the Hb occupancy to approximately 54%. These projections were obtained from a population pharmacokinetic (PPK) model using the data from all 6 participants who have been enrolled in this study.

The Extended Treatment Period is being added to explore the safety and tolerability of these loading and maintenance dose levels. It is believed that higher Hb occupancy will translate to clinical benefits such as improved signs and symptoms of anemia, potentially reduced VOCs, and improved overall well-being in participants with SCD. To assess the full potential of this new agent, a formal multicenter dose-ranging study is being planned to evaluate higher doses of GBT021601, and it is critical to determine to safety/tolerability and effects on Hb occupancy and other hematological parameters at this proposed regimen (300 mg bid x 4 days plus 150 mg QD for 81 days).

CCI [REDACTED]

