At the Week 13 Visit, participants may be dose escalated to receive a loading dose and subsequent maintenance dose based on a predicted target of >30% occupancy/modification as determined by the PK results of GBT021601-011 and Part A of this study. Week 16 will be the end of treatment (EOT) Visit and participants will return to the clinical site for the end of Part B Safety Follow-up Visit approximately 5 half-lives after the final dose at Week 16. The elimination half-life will be determined from the PK results from the GBT021601-011 study and Day 42 following a single dose of 100 mg. It is anticipated that 5 half-lives will not exceed 120 days after the final dose.

Participants will not be confined at the CRU during the Multiple Dose Period.

Based on the findings from Dose Levels 1 and 2, there were no significant safety concerns related to GBT021601 and based on PK modeling, the planned doses for Part C are expected to result in Hb occupancy of approximately 54%.

Eligible participants may proceed with an Extended Treatment Period of at least 6 weeks, with a 300 mg loading dose twice daily over 4 days and subsequent maintenance dose of 150 mg once daily starting from Part C Day 1 and continuing through Part C Week 6. **CCI** [REDACTED] **CCI** [REDACTED]
[REDACTED]
[REDACTED]
[REDACTED]
[REDACTED]
[REDACTED]

The EOB Visit will occur after completion of the Multiple Ascending-dose Period as presented in [Table 3-3](#). The EOS Visit will occur after completion of the Extended Treatment Period as presented in [Table 3-4](#).

Figure 3-1: Study Schematic for GBT021601-012:

[figure not shown]

Table3-1: Schedule of Assessments for Single-dose Period (Part A)

	Screen n	Confinement					Outpatient				
		-1	1	2	3	4	7	14	21	28	42
Study Day	-30 to -2										
Informed consent	X										
Eligibility assessment	X	X									
Medical history ^a	X										
Physical examination ^b	X	X					X				
Height	X										
Weight	X	X					X	X	X	X	X
Vital signs ^c	X	X	X	X	X	X	X	X	X	X	X
12-lead ECG (triple tracing) ^d	X	X	X	X	X	X		X		X	
Study drug administration			X								
Serology (hepatitis A, B, C) HIV, SARS-CoV-2	X										
Alcohol (breath or blood) and urine drugs of abuse screen	X	X									
Hematology, Serum chemistry, and Lipid Panel ^e	X	X		X		X		X		X	
aPTT, INR, PT	X										
Serum erythropoietin		X	X			X		X		X	
SCD documentation or Hemoglobin Electrophoresis	X										
eGFR ^f	X	X									
Urinalysis	X	X				X					

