3.6 Study Drug Administration

GBT021601 will be administered orally. For the single-dose period, participants will fast at least 10 hours before and for at least 4 hours after study drug administration. Water will be allowed as desired except for 1 hour before and 1 hour after study drug administration.

Part A: Single oral dose of GBT021601 100 mg on Day 1.

Part B: The starting multiple ascending doses will be chosen to achieve ~20% to 30% Hb occupancy with once daily treatment (Dose 1) proceeded by loading doses. In addition, this dose level is predicted to achieve a Cmax at steady-state no higher than 2-fold the Cmax observed and well tolerated following single dose or multiple doses in study GBT021601-011. For the second dose level (Dose 2), the target of >30% Hb occupancy will be used as determined by the PK results found in GBT021601-011 and results from Part A of this study given at Weeks 8-13.

Part C: 300 mg loading dose twice daily over 4 days subsequent maintenance dose of 150 mg once daily starting from Day 5 and continuing through Week 6.

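### Protocol and SAP give conflicting first days for Part C maintenance dosing: three places say Day 1, SAP 3.6 says Day 5, and others place it after the four-day load.

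*Protocol*

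**What the plan says.** Part C has a loading dose of 300 mg twice daily for four days and a maintenance dose of 150 mg once daily. The documents give the first day of maintenance in different ways.

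**Day 1 wording**
- Protocol synopsis, Study Design: "subsequent maintenance dose of 150 mg once daily starting from Part C Day 1 and continuing through Part C Week 6".
- SAP 3.1: "maintenance dose of 150 mg once daily starting from Part C Day 1 and continuing through Part C Week 6".
- SAP 3.8 repeats the synopsis wording.

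**Day 5 wording**
- SAP 3.6: "subsequent maintenance dose of 150 mg once daily starting from Day 5 and continuing through Week 6".

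**Maintenance after the load, with no day number**
- Protocol synopsis, test product paragraph: "the loading dose will be 300 mg, twice daily, for 4 days followed by a once daily maintenance dose of 150 mg".
- Protocol Table 4 footnote d, from the Day 1 visit: "loading dose of 300 mg twice daily for four days followed by a maintenance dose of 150 mg once daily". SAP Table 3-4 footnote d says the same.
- Protocol 3.4.2.3: the 150 mg daily period is "preceded by a loading dose of 300 mg, given twice daily over 4 days".
- Protocol 4.3.3 calls maintenance subsequent to the load, gives no start day, and defers to Table 4.

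**The concern.** The load begins on Part C Day 1. A sentence that also starts maintenance on Day 1 can be read as adding 150 mg to the load on each of the first four days. The same sentences call the maintenance dose subsequent, so the adjective and the stated day point in different directions. SAP 3.6 names a different day outright.

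This is a dosing instruction, and it is followed largely outside the clinic. Under Table 4 footnote e, the diary covers all doses except the first loading dose and any maintenance doses given in the clinic. Table 4 has no visit between Day 1 and Week 2 (Day 14 ± 3 days), and the first diary is collected at Week 2. In Part C the Safety Monitoring Committee meets only ad hoc (protocol 5.6). During the load, the written instruction is therefore the main safeguard. Protocol 3.4.2.3 gives the safety and tolerability of these loading and maintenance levels as the reason for adding Part C, so the regimen needs to be described in one way.

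**Working it through.** The documents state no total daily or cumulative Part C dose, so there is no planned figure to reproduce. The totals below follow from the stated regimen.

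**Inputs:** load 300 mg, twice daily, 4 days; maintenance 150 mg once daily; end of treatment at Week 6, Day 42 ± 3 days (protocol synopsis and Table 4).

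**Days 1-4**
- Maintenance after the load: 300 × 2 = 600 mg/day; 600 × 4 = 2400 mg.
- Maintenance from Day 1, read literally: 600 + 150 = 750 mg/day; 750 × 4 = 3000 mg.
- Ratio: 750 / 600 = 1.25, or 25% more.

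**Through Day 42**
- Maintenance from Day 5: 42 − 4 = 38 maintenance days; 2400 + 38 × 150 = 8100 mg.
- Maintenance from Day 1: 42 maintenance days; 2400 + 42 × 150 = 8700 mg.
- Difference: 600 mg; 600 / 8100 = 7.4%. If the Week 6 visit falls on Day 39 or Day 45, the difference is still 600 mg, against 7650 mg (7.8%) or 8550 mg (7.0%).

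**Doses outside the clinic:** the load is 2 × 4 = 8 doses. Only the first is excepted from the diary, so up to 7 of the 8 are taken away from the clinic.

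**Consequence for the planned summaries**
- Concentrations: SAP 6.1 does not summarise Part C concentrations up to Week 2. The only scheduled PK visit in Days 1-4 is Day 1.
- Safety: SAP 7.17 summarises by part or overall and by visit, and SAP 7.17.1 summarises treatment-emergent events by part and overall. Neither specifies a split of events by dosing phase.
- PD: hemoximetry and RBC deformability go to a separate report (SAP 6.4).
- General rule: SAP 7.1 provides for PK, PD and safety summaries by loading and maintenance doses, or overall, as applicable. It gives no boundary between the two phases. The start day matters to the analysis only if that split is used.

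**The case against.** The best answer is that the intended order is plain. The Day 1 sentences themselves call maintenance subsequent to a four-day load. Their closing phrase can be taken to describe the whole regimen, which does start on Day 1 and run to Week 6. Within the protocol, only one synopsis sentence carries the Day 1 wording. The other synopsis paragraph, 3.4.2.3 and Table 4 footnote d are all sequential, and 4.3.3 defers to Table 4. No passage describes taking both doses together. This stands as far as it goes: 750 mg/day is the literal reading of three sentences, not an alternative of equal weight. It does not remove the conflict, because the SAP names Day 5 in one section and Day 1 in two others, and no text says which governs.

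A second answer is that a misreading would come to light. Footnote e requires the actual time of every dose to be recorded, and protocol 7.6 requires dispensing records. This also stands, but only in retrospect: actual dosing can be reconstructed from Week 2, after the load is over.

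A reader might go further and infer that Days 1-4 data would be attributed to the wrong phase throughout the analysis. The documents do not support that, for the reasons given in the working.

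A reader might also infer a lasting difference in exposure. The documents state no half-life. As an illustration, take one compartment with an assumed half-life of 15 to 24 days; the interval from Day 112 to the Day 218 visit, set at about five half-lives, implies (218 − 112) / 5 = 21.2 days. The literal reading then raises body load by about 25% at the end of Day 4, 13% to 14% at Day 14, 6% to 8% at Day 28 and 3% to 5% at Day 42. The largest figure falls where no sample is scheduled, and all of them depend on the assumed model and half-life.

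**Conclusion.** The inconsistency is real and lies within each document as well as between them. It should be corrected because it concerns a dosing instruction followed mostly at home. It is not evidence that the plan intends concurrent dosing. The size on Days 1-4 is 600 against 750 mg/day (2400 against 3000 mg); the higher figure assumes that the Day 1 wording is taken literally and the word subsequent is disregarded. The effect on the planned analyses is small and is confined to any loading/maintenance split made under SAP 7.1. The dispensing instructions and diary are not among the documents, so whether they already settle the matter is unknown. Which start day is right is for the sponsor to say.

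**What to change.** Reconcile these places to one stated first day of maintenance dosing, chosen by the sponsor:
- protocol synopsis, both the Study Design and the test product paragraphs;
- protocol Table 4 footnote d;
- SAP 3.1, 3.6 and 3.8;
- SAP Table 3-4 footnote d.

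Carry the same day into the dispensing instructions and the participant diary. If any Part C summary is split by loading and maintenance, add a sentence to SAP 7.1 setting the boundary at each participant's recorded first maintenance dose. If Part C dosing is already complete, the study report should describe the regimen as recorded.

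The cost is wording changes in the two documents and a check of the dispensing and diary text. No procedures, visits or samples are added, because dose times are already to be recorded.
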